**12.10c) The plan to protect the identifiers from improper use and disclosure is adequate.**

Agree  Disagree

Describe the plan

Participant identity will be coded immediately upon entry into the study, and neither the participants' names nor any identifying information will be present in the data set. Study records entered into a computer system will be assigned code numbers and will not be individually identifiable. The computerized system where data will be stored will not leave the protected VA environment unless the data storage components are removed or destroyed. Data collected in other areas (testing rooms) will be stored in a locked cabinet that is maintained in a locked office (room 332 VMRF or room 306B VMRF) within the VA. Computer data will be protected by strong passwords and accessible only by study personnel. Data will be regularly backed up and the backup stored in a separate locked area controlled by the investigator (room 332 VMRF or room 306B VMRF).

The key that relates the code numbers to the individuals will be stored in a stand-alone (non-networked) computer system that is maintained in a locked office within the PI's lab space in Building #13 of the VA San Diego, protected by strong passwords, and accessible only by approved study personnel. This system will not leave the protected VA environment unless the data storage components are removed or destroyed. Hardcopy SI will also be stored for backup purposes in the PI's laboratory within Building #13 of the VA San Diego, in a locked cabinet. Code-numbered data will be stored in a separate filing cabinet under lock and key in Building #13. All SI related to this study will be destroyed in accordance with RCS-10 and under the direction of the VA Records Control Manager.

In the event of a real or suspected breach of security, the VA Police, the VA Information Security Officer, and the VA Privacy Officer will be notified.

**12.10d) An adequate plan to destroy the identifiers at the earliest opportunity consistent with conduct of the research, unless there is a health or research justification for retaining the identifiers or such retention is otherwise required by law.**

Agree  Disagree

12.10d2) Describe the plan:

SI, such as subject's medical diagnosis, will be used for the purpose of enrollment and subject's personal information, such as age, gender, and education, will be used to characterize the subject pool utilized in this study. Addresses and telephone numbers will also be collected as a means to contact the subjects for follow-up when indicated. All data used in this study will be de-identified and linked to SI by a subject number. Hard copy SI will also be stored for backup purposes in the PI's lab, within Building #13

Data will be destroyed according to RCS-10 under Records Control Manager guidance.

**12.10e) By signing this protocol for submission, the PI is providing written assurance that the PHI will not be reused or disclosed to any other person or entity, except as required by law, for authorized oversight of the research project, or for other research for which the use or disclosure of protected health information would be permitted by the Privacy Rule. 38 U.S.C. 7332 Information: If the waiver of HIPAA authorization is for the use of 38 USC 7332 information (applicable to drug abuse, alcohol abuse, HIV infection, and sickle cell anemia records), by signing this protocol for submission the PI is providing written assurance that the purpose of the data is to conduct scientific research and that no personnel involved may identify, directly or indirectly, any individual patient or subject in any report of such research or otherwise disclose patient or subject identities in any manner. (Ref: 38 U.S.C. 7332(b)(2)(B))**

Agree  Disagree

#### **12.10f) The research could not practicably be conducted without the waiver or alteration.**

Agree  Disagree

12.10f2) Describe how the waiver/alteration enables the research to be conducted

Without the phone screen for contact information and brief exclusionary criteria there would be no feasible way for us to send participants directions and appointment confirmation. There would also be potential for many participants to travel to VASDHS to participate in the study, sign a consent form only to find out they are ineligible for the study and be excused. This would waste the time of the participant as well the VASDHS.

The ability to contact VA patients directly will allow us to recruit more veterans to be enrolled in the study. Additionally, the ability to access medical diagnoses consistent with study inclusion criteria will reduce burden on potential study participants as we will not have to schedule additional appointments or testing to verify diagnoses of these patients. This will also reduce burden on clinicians who may not have time to recruit patients during busy clinic duties and will expand access to these services for Veterans who may not have any upcoming clinic visits in the near future.

#### **12.10g) The research could not practicably be conducted without access to and use of the PHI.**

Agree  Disagree

12.10g2) Describe why it would be impracticable to conduct this research without the PHI described 12.10a. (v3 /8/18)

- 1) The data collected by the waiver/alteration (phone screen) is necessary to determine study eligibility.
- 2) The research candidate form allows research assistants on this protocol to call the patient and recruit them for the study, if interested and eligible. This form provides the means to contact the patient.
- 2b) The patient's name and contact information will be required for calling patients who were not presented the opportunity to sign the form (this includes subjects previously enrolled in other studies). The patient's phone number will be required to contact the patient.
- 3) Accessing medical diagnoses in CPRS allows the research team to focus recruiting attention on those who are likely eligible (i.e., a veteran with Parkinson's disease). Additionally, having access to this information reduces participant burden; Veterans will not be scheduled for multiple testing sessions (through research and clinical services) and we will not have to schedule additional appointments or additional testing to verify diagnoses, as they are already listed on file. Furthermore, this will allow us to expand recruitment to Veterans who may not otherwise be reached within targeted clinics at VASDHS

### **Section 13 - Alternatives to Participation**

#### **13) Describe the alternatives to participation in this research study (see ? for guidance)**

The alternative to participating is to not participate.

### **Section 14 - Potential Risks**

#### **14) Describe any potential or known risks or discomforts and assess their likelihood and seriousness (see ? for guidance)**

This study does not present any major or serious risks beyond those commonly associated with standard behavioral interventions and neuropsychological testing. The neuropsychological tests and motor examinations are typically used in the clinical management of PD patients. Though the risks are relatively minimal, all participants will be informed of the possibility of experiencing potential risks during the informed consent process.

Risks involved with neuropsychological testing and the interventions (MBSR and Psychoeducation/ Supportive Care) are minimal; however, there is the potential that participants may become fatigued, nervous, bored and/or frustrated during the neuropsychological testing (i.e., cognitive assessment and self-report questionnaires) sessions and/or interventions (MBSR or Psychoeducation/Supportive Care). There is also a possible risk that the interventions may cause an increase in negative emotions due to becoming more aware of certain aspects of their disease or lives. There is no requirement to share personal or mental health information but there may be a risk of loss of confidentiality due to the interventions happening in a group setting. Additionally, individuals may also experience emotional discomfort while answering self-report /emotion/mood questionnaires.

Given the age and medical condition (i.e., Parkinson's disease) of the participants, it is possible that individuals may experience medical or psychological changes unrelated to the study that would necessitate early termination of the study.

## Section 15 - Risk Management

**15) Describe the procedures for protecting against or minimizing any potential risks/discomforts, and the adequacy of resources for conducting the study and resources participants may need as a consequence of the research. When applicable, include detail of the following safety measures:** (a) The type of safety information to be collected, including AEs; (b) Frequency of safety data collection; (c) Frequency or periodicity of review of cumulative safety data; (d) Statistical tests for analyzing the safety data to determine if harm is occurring; and (e) Conditions that trigger an immediate suspension of the research. See ? for further requirements.

This study does not present any major or serious risks beyond those commonly associated with standard behavioral interventions and neuropsychological testing. The neuropsychological tests are typically used in the clinical management of PD patients. Though the risks are relatively minimal, all participants will be informed of the possibility of experiencing potential risks during the informed consent process.

To ensure the safety and comfort of all subjects, rest breaks are offered during the neuropsychological evaluations and the intervention groups. Participants will also be free to ask for additional rest breaks or other accommodations to increase tolerability of testing and participation. Participants will be permitted to discontinue the testing or intervention at any time for any reason as stipulated in the Human Subjects IRB consent form. All group participants, however, will be strictly instructed on the need for confidentiality related to group membership and group proceedings.

Given the age and medical condition (i.e., Parkinson's disease) of the participants, it is possible that individuals may experience medical or psychological changes unrelated to the study that would necessitate early termination of the study. If the individual situation warrants, participants may be able to rejoin a later group. Because both interventions (Psychoeducation/Supportive Care and MBSR) are not group therapy, there is no requirement that individuals will share personal and/or mental-health information. However, should any information be conveyed that causes study staff to be concerned about that participant's psychological well-being, appropriate referrals to the VA Geropsychiatry Clinic may be provided to veterans, or other appropriate community resources for veterans and non-veterans will be provided.

Due to the fall risk associated with individuals with PD, we will use the baseline MDS-UPDRS falling item (#13) in which a history of falls is categorized on a Likert scale from 0 (none) to 4 (falls >once per day). A history of falls as assessed by the MDS-UPDRS appears to be one of the best predictive methods of subsequent falls at this time. Those individuals who endorse a history of falling or score >0 on the MDS-UPDRS falling item, will be closely monitored. Should an individual who is at risk for falling be identified, we will offer assistance during each class to escort the individual to and from the intervention room, from their vehicle, as well as to and from the bathroom, if needed. As standard in MBSR, all participants will be encouraged to work within their own personal limits and preferences. Alternatives to the standard exercises will be offered. These alternatives include sitting in a chair in lieu of floor exercises; lying down for standing exercises; omitting certain (e.g., walking) meditations; and/or visualizing the movements in lieu of acting them out. These options are standard in MBSR and have also been implemented in other trials of MBSR for PD.

Suicidal ideation (SI) will be assessed by Beck Depression Inventory (BDI-II) item #9 at each assessment (i.e., pre-, post-, 6- and 12-months). Should an individual indicate  $\geq 1$  on the BDI-II item 9, the tester will immediately notify a licensed clinician on the protocol. The clinician will

conduct a thorough clinical evaluation of SI to determine appropriateness to continue in the study and provide any necessary referrals. In addition, each week during the intervention, the participants will complete a brief form which will contain two questions regarding changes in mood and medications. Should a participant indicate mood changes, mood and SI will be evaluated by a licensed clinician to determine appropriateness to continue in the study.

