Those who meet criteria will be administered the pre-intervention neuropsychological battery within approximately one week prior to beginning the group by an examiner who will be blinded to group assignment. Participants will be group randomized to one of two 8-week conditions (i.e., 6-8 participants assigned in groups via R randomizer to either Mindfulness Based Stress Reduction (MBSR) or Psychoeducational Supportive Care). All activities will be conducted on the VA San Diego campus. MBSR and Psychoeducational Supportive Care groups will each consist of approximately 6-8 individuals with PD and be led by a trained instructor who is not involved in the clinical care or assessment of these participants. Participants will meet in groups for 2.5 hours once per week for eight weeks, with a 2.5 hour session ("retreat") between weeks 6 and 7. Each week and at the start of group, all participants will complete a brief form regarding changes in mood and medications. Any changes in mood will be addressed by clinicians on the protocol to assess for SI (please see MCM 11-24 Suicidality attached to protocol). We will offer assistance during each session to escort those who are at risk for falling (i.e., UPDRS fall item #13 > 0) to the bathroom and to and from their vehicle as appropriate.

All participants will be administered a battery of neuropsychological tests to measure HRQoL, cognition (e.g., executive function, attention, memory), and mood (i.e., anxiety, depression, and apathy), as well as motor symptoms, disease severity, and mindfulness engagement/practice. The UPDRS Part-III/Hoehn and Yahr Score (HYRS), which assess level of motor function and characterizes disease severity, will also be administered by study staff, certified in UPDRS administration, at their baseline assessment. If we are unable to obtain this score, we will obtain a ROI to access their UPDRS exam score(s) and HYRS. Tests will be administered at baseline, 8 weeks (post-treatment), and 6- and 12-months (follow-up assessments). Breaks will be offered and given during the assessment as needed. Study questionnaires are attached to the protocol submission.

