Following the intervention and 6- and 12-months post-intervention, PD participants will be re-tested by a group-blinded research assistant. The UPDRS Part-III/HYRS will also be administered by study staff, certified in UPDRS administration, at the 12-month follow up appointment as well. Total participation time is 2-3 hours per session x 4 total sessions (-pre, -post, -6, and -12 month follow up). To better retain participants throughout the 12-month trial period, we will implement friendly reminder calls at 2-months and 1-month prior to each testing session as well as send a reminder letter with pertinent information (e.g., directions) 2-3 weeks prior to their appointment. In addition, MBSR will be offered to the Psycheducational Supportive group participants upon study completion.

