#### Data Security

A tertiary risk might include unintentional disclosure of confidential test information, but confidentiality will be strictly maintained in data storage, manipulation, and presentation.

This study will collect PHI (i.e., data, in any format, which requires protection due to the risk of harm that could result from inadvertent or deliberate disclosure, alteration or destruction) from all participating subjects. PHI used in this study will include individually identifiable medical and health data and personal information, such as age, educational level, gender and ethnicity. Subjects' medical diagnoses will be used for the purpose of enrollment and personal information, such as age, gender, and education, will be used to characterize the subject pool utilized in this study. Addresses and telephone numbers will also be collected as a means to contact the subjects for follow-up when indicated. Participant identity will be coded immediately upon entry into the study, and neither the participants' names nor any identifying information will be present in the data set. The computerized system where data will be stored will not leave the protected VA environment unless the data storage components are removed or destroyed. Data collected in other areas (testing rooms) will be brought to the lab and locked away each night. Only approved study personnel will have access to this information.

Presentation of the results will involve group data and the subjects' identity will not be disclosed. In the event of a real or suspected breach of security, the VA Police, Information Security Officer, and the Privacy Officer will be notified. Overall, the proposed study poses no significant increase in risk than what would normally be present in proper clinical management of and frequently prescribed psychological treatment and medical procedures (e.g., UPDRS motor exam) for PD patients.

Adverse Events (AE) and Serious Adverse Events (SAE), as defined below, will be monitored throughout the study duration.

An Adverse Event (AE) is any untoward physical or psychological occurrence in a human subject participating in research. A related AE, death, or problem is an AE, death, or problem that may reasonably be regarded as caused by, or probably caused by, the research.

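### Fall precautions are set from baseline fall history, and no scheduled question updates fall status during the eight weekly sessions and the retreat

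*Combined protocol and SAP*

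**What the plan says.** Section 15 (Risk Management) sets out the fall precaution. On the instrument it says "we will use the baseline MDS-UPDRS falling item (#13) in which a history of falls is categorized on a Likert scale from 0 (none"), the top of the scale being 4. People who endorse a fall history or score above 0 are to be closely monitored. The response follows: "Should an individual who is at risk for falling be identified, we will offer assistance during each class", covering the way between vehicle, intervention room and bathroom. Section 9 (Assessments and Intervention) gives the same escort offer and ties it to the item: "to escort those who are at risk for falling (i.e., UPDRS fall item #13 > 0").

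The baseline battery is given "within approximately one week prior to beginning the group". The groups then meet for 2.5 hours once a week for eight weeks, with one 2.5-hour retreat between weeks 6 and 7.

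One form is scheduled during this period. Section 9 says: "Each week and at the start of group, all participants will complete a brief form regarding changes in mood and medications". Section 15 confirms its length: "the participants will complete a brief form which will contain two questions regarding changes in mood and medications".

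The test battery is repeated at 8 weeks, 6 months and 12 months. For the UPDRS, the only later administration named is at the end: "The UPDRS Part-III/HYRS will also be administered by study staff, certified in UPDRS administration, at the 12-month follow up appointment as well". Separately, the Data Security part of Section 15 states: "Adverse Events (AE) and Serious Adverse Events (SAE), as defined below, will be monitored throughout the study duration".

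**The concern.** The plan treats past falls as one of the best available predictors of further falls. On that reasoning, a first fall during the group phase is exactly what should switch the precaution on. Yet the scheduled information on falls stops at baseline.

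The plan handles its other singled-out risk differently. Suicidal ideation is asked about at every assessment, and the weekly mood question prompts a clinician's evaluation. Fall risk has no such update.

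At stake is the safety of participants coming to, moving about and leaving the sessions. Someone who scored 0 at baseline and then begins to fall meets the plan's own reason for an escort, but no scheduled step tells staff so.

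**Working it through.** The plan gives no figure to reproduce. The check sets the schedule beside the fall-related text and counts.

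**Inputs**
- Participants: 88 (Section 2a; Section 9, Participants).
- Meetings: 8 weekly sessions plus 1 retreat, each 2.5 hours (Section 9, Assessments and Intervention).
- Baseline: about 1 week before the first session (same section).
- Start-of-group form: 2 questions, on mood and medications (Section 15).

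**Time on site.** 8 + 1 = 9 meetings; 9 × 2.5 h = 22.5 h per participant.

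**Age of the baseline answer at session 8.** About 1 week before session 1, plus 7 weeks from session 1 to session 8, gives about 8 weeks. This assumes the retreat does not displace a weekly session. The answer could be older for anyone who leaves and rejoins a later group, which Section 15 allows, because the documents do not say that the fall item is then repeated.

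**Fall questions scheduled after baseline and through the last meeting**

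| Scheduled contact | Content stated | Fall question |
|---|---|---|
| Start-of-group form, 8 sessions | Mood, medications | None |
| Retreat | No form specified | None |
| Battery at 8 weeks, 6 and 12 months | After the group phase | Outside the window |
| UPDRS Part III and Hoehn and Yahr, 12 months | After the group phase | Outside the window |

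Total: 0.

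**Volume of forms, at full attendance (upper bounds)**
- All participant-meetings: 88 × 9 = 792.
- Weekly sessions, where the form is already completed: 88 × 8 = 704.
- Retreat, where its use is not stated: 88 × 1 = 88.
- Check: 704 + 88 = 792.

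These counts measure exposure and paperwork, not harm. They include participants already flagged at baseline.

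**Unscheduled routes by which a new fall could surface**
- Adverse events are monitored throughout, and a fall fits the definition. The text does not say how events are elicited, and falls are not among the potential risks listed in Section 14 or the potential adverse events named in Section 15.
- The escort wording in Section 15 covers anyone identified as at risk and sets no time limit. No later means of identification is given.
- Groups are small (6 to 8) with a trained instructor, and participants may ask for accommodations.

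All of these depend on a fall being mentioned or seen. A fall at home between sessions is the easiest to miss.

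**The case against.** The strongest reply is that the precaution is not strictly frozen at baseline. Only the fall item is dated. The escort offer and the criterion of an endorsed fall history carry no date, so staff may act on a fall they hear of later. Other safeguards also exist:
- Eligibility requires walking or standing without dependence on an assistive device, and the phone screen asks about movement problems.
- Section 9.11 has the facilitator note each person's participation.
- The medication question is a weekly prompt about health changes.
- Exercise alternatives are offered to everyone, whatever their fall score.
- An escort is only an offer, which anyone who feels unsteady can request.

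Much of this stands and limits the weight of the point. It does not close the gap, because none of these steps asks about falls. The facilitator sees what happens in the room, not at home. Section 15 attaches no fall-related action to a medication change. Exercise alternatives do not help on the way to the car.

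Three further points are fair. Naming only Part III at 12 months does not prove that the fall item is omitted then, since Section 9 also names only Part III at baseline, where the item clearly is used; that visit is in any case outside the period at issue. The participant-meeting counts say nothing about how many new fallers would be missed. And the questionnaires attached to the submission are not reproduced, so an unseen form could ask more; for the weekly form, however, Section 15 states its content explicitly.

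**Conclusion.** The concern holds, as a modest matter of participant safety for consideration. After baseline and through the last of 9 meetings, the documents schedule 0 fall questions, and the baseline answer is about 8 weeks old by session 8. Later identification is possible but relies on a fall being volunteered or noticed.

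How many participants would newly qualify for the escort is unknown, because the documents give no fall rate; it may be few. The conclusion rests on the stated content of the weekly form and the stated assessment schedule. It has no bearing on the primary outcome, the analysis or the sample size.

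**What to change.** Add one yes/no line to the start-of-group form asking whether the participant has fallen since the last session, and give the form at the retreat too. State that a yes from someone not already flagged starts the close monitoring and escort offer of Section 15 from that session on. The baseline item, escort procedure, exercise alternatives, assessment battery and adverse event handling stay as they are.

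The cost is one line on up to 704 existing forms, up to 88 retreat forms if none are used there now, and a short IRB amendment. More adverse event reports will follow, since Section 15 requires one for each event. That includes repeat falls in known fallers, whose precautions would not change. The investigator should weigh that reporting load, but no new visit, instrument or analysis is needed.
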